4.12.5.1 Pharmacodynamics Analysis and Tables, Figures, and Listings

All PD analyses will be performed on the PD Analysis Set and will be reported by each cohort. Observed values and changes from baseline in plasma concentrations of PPi, PLP, PL, and PA versus time will be presented graphically by treatment over time compared with placebo-treated participants.

The PD parameters for ALXN1910 will be evaluated over time for Japanese and non-Japanese participants (Cohort 2 versus Cohort 4) on active treatment by using MMRM model with cohort, visit, and cohort by visit interaction as fixed effects, participant as a random effect, and baseline value as a covariate. The unstructured covariance structure will be employed; however, if the model fails to converge, Toeplitz, heterogeneous compound symmetry, and compound symmetry covariance structure will be applied in the order listed until the model converges.

In the case that all covariance structures fail to converge, the analysis of variance statistical model with baseline and cohort as the fixed effects will be used. In addition, the Japanese versus non-Japanese cohorts will be evaluated using descriptive statistics; for each cohort, the geometric means and the associated 95% CIs of difference of PD parameters in observed value and CFB value will be reported. Figures of absolute values and change from baseline over time may be produced if needed.

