# 1.3. Schedule of Activities

The SoAs for all cohorts from Screening through Day 5 and from Day 6 through Day 75 are presented in Table 2 and Table 3, respectively.

Table 2: Schedule of Activities – Single Ascending Dose Cohorts (Screening through Day 5)

Study Day a	Screen -ing	Day -1				Day 1				Da	y 2	Da	y 3	Da	y 4	Day 5
Assessments	D -29 to D-2	Admit	Pre- dose	0 h I/ SOI	30 min post I/SOI	2 h post I/SOI	4 h post I/SOI	8 h post I/SOI	12 h post I/SOI	24 h post I/ SOI	36 h post I/ SOI	48 h post I/ SOI	60 h post I/ SOI	72 h post I/ SOI	84 h post I/ SOI	96 h post I/SOI
Status (OP or CRU)	OP		•	•	•			(	CRU	•		•	•	•		
Admission		X														
Discharge																$X^b$
Informed consent c	X															
Inclusion/exclusion d	X	X														
Medical history e	X															
Demographics	X															
Height, weight, and BMI f	X	X														
Hepatitis B and C screen	X															
HIV (Types 1 and 2) screen	X															
Follicle-stimulating hormone g	X															
Urine alcohol test	X	X														
Urine drug screen	X	X														
Serum pregnancy test h	X															
Urine pregnancy test h		X														
Randomization i			X													
Study intervention administration (ALXN1910 or placebo)				X												
Injection/infusion site evaluation j				X			X			X		X		X		X
Physical examination	X	X														

**Table 2:** Schedule of Activities – Single Ascending Dose Cohorts (Screening through Day 5)

Study Day a	Screen	Day -1				Day 1				Da	ıy 2	Da	y 3	Da	y 4	Day 5
Assessments	-ing D -29 to D-2	Admit	Pre- dose	0 h I/ SOI	30 min post I/SOI	2 h post I/SOI	4 h post I/SOI	8 h post I/SOI	12 h post I/SOI	24 h post I/ SOI	36 h post I/ SOI	48 h post I/ SOI	60 h post I/ SOI	72 h post I/ SOI	84 h post I/ SOI	96 h post I/SOI
Status (OP or CRU)	OP			I	I.	I.		(	CRU	I		I	I	I		1
Brief physical examination k										X		X				X
Vital sign measurements 	X		X		X	X	X	X	X	X		X		X		X
ECG m	X		X		X	X	X	X	X	X	X	X		X		X
Chemistry n	X	X								X						X
Hematology n	X	X								X						X
Coagulation n	X	X								X						X
Urinalysis n	X	X								X						X
PK°			X		X	X	X	X	X	X		X		X		X
PD (PPi, PLP, PL, and PA)			X							X		X				X
Urine for calcium, phosphorus, and creatinine p			X							X		X				X
Immunogenicity samples q			X													

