# 7.3. Participant Discontinuation/Withdrawal from the Study

- All efforts should be made to ensure participants are willing to comply with study participation prior to conducting the screening procedures.
- The study staff should notify Alexion and their site monitor of all study withdrawals as soon as possible. The reason for participant discontinuation must be recorded in the source documents and eCRF.
- A participant may withdraw from the study at any time at their own request or may be withdrawn at any time at the discretion of the Investigator for safety, behavioral, compliance, or administrative reasons. This activity is expected to be uncommon.
- At the time of discontinuing from the study, an early discontinuation visit should be conducted that includes the EOS assessments shown in the SoA, if possible (Section 1.3).
- All efforts will be made to contact participants who withdraw/are withdrawn from the study via phone for a safety follow-up call approximately 30 days (4.5 half-lives) after their dose to assess AEs.

- The first participant in each cohort to withdraw/be withdrawn from the study prior to completion of the EOS assessments may not be replaced; subsequent participants in that cohort to withdraw/be withdrawn before EOS completion will be replaced.
- If the participant withdraws consent for disclosure of future information, Alexion may retain and continue to use any data collected before such a withdrawal of consent.
- If a participant withdraws from the study, the participant may request destruction of any samples taken and not tested, and the Investigator must document this in the site study records.

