3 INVESTIGATIONAL PLAN

3.1 Overall Study Design and Plan

This is a Phase 1, randomized, double-blind, placebo-controlled study designed to evaluate the safety, tolerability, PK, PD, and immunogenicity of SADs of ALXN1910 SC and a SAD of ALXN1910 IV in up to approximately 48 healthy adult participants across treatment cohorts (up to approximately 36 participants to receive ALXN1910 and up to approximately 12 participants to receive placebo) (Table 1). Of the 48 participants, 8 will be of Japanese descent, defined as those participants whose parents and grandparents are both Japanese and who have spent less than 10 years outside of Japan.

Cohortª	Number of Participants (ALXN1910:Placebo)	Route of Administration	Dose	Number of Doses/Dose Interval
1	8 (3:1)	IV ^b	5 mg	Single dose
2	8 (3:1)	SC	15 mg	Single dose
3	8 (3:1)	IV ^b	15 mg	Single dose
4	8 (3:1) (Japanese participants)	SC	15 mg	Single dose
5	8 (3:1)	SC	45 mg	Single dose
6	8 (3:1)	SC	135 mg	Single dose

 Table 1
 Planned ALXN1910-HV-101 Dosing Cohorts

^a Cohort 3, Cohort 4, and Cohort 5 can be initiated in parallel after dose escalation decision following SRC review of Cohort 2 safety and PK data.

^b Slow IV infusions (rate of infusion = 6 mL/h) using a controllable infusion pump. The pharmacy manual will include details regarding infusion rate and duration.

Abbreviations: IV = intravenous; PK =pharmacokinetic; SC = subcutaneous; SRC = Safety Review Committee

[figure not shown]
For this FIH study, 8 participants will be randomly assigned in a 3:1 ratio to treatment and placebo in each of the 6 cohorts with escalating doses of 5 mg IV (Cohort 1), 15 mg SC (Cohort 2), 15 mg IV (Cohort 3) in parallel with 15 mg SC in Japanese participants (Cohort 4) and 45 mg SC (Cohort 5), followed by 135 mg SC (Cohort 6). The first 2 participants randomized to each cohort will be dosed as a sentinel pair, with 1 participant on active treatment and 1 participant on placebo. This dosing strategy is justified given the large exposure margins (approximately 15-fold at the highest planned single dose of 135 mg SC).

Participants who meet the qualifications for the study based on screening will be admitted to the CRU the day prior to dosing (Day -1) to undergo Check-in assessments per the applicable SoA (Section 6.1).

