The PK parameters for ALXN1910 will be evaluated for Japanese and non-Japanese participants (Cohort 2 versus Cohort 4) on active treatment, using an analysis of variance statistical model with cohort as the fixed effects on the natural logarithms of the data. In addition, the Japanese versus non-Japanese cohorts will be evaluated using descriptive statistics; for each cohort, the geometric means and the associated 95% CIs of difference of PK parameters will be reported.

PK parameters will be separately analyzed using a mixed effects model. The dependent variable will be the log-transformed PK parameters of interest (AUC $_{\infty}$, AUC_t and C_{max}) and the independent variables will include a fixed effect for ethnicity (Japanese vs non-Japanese) and participant as a random effect.

The estimated difference and CI obtained on the log scale will be exponentiated to provide an estimate of the Japanese to non-Japanese ratio and its associated 95% CI. Estimates of between -participant variability (%CV) will also be provided.

Plots of adjusted GMR of Japanese to non-Japanese together with 95% CIs will be produced.

SAS code for this analysis is mentioned in Section 6.5.

4.12.5 Pharmacodynamic Analysis, Concentration, and Parameter TFLs, and Statistical Analysis of Pharmacodynamic Parameters

Individual participant PPi versus time profiles values, both observed and change from baseline, will be calculated by Charles River Lab and Individual participant PLP, PL, PA versus time profiles values, both observed and change from baseline, will be calculated by PPD Laboratories respectively. Baseline observed, observed, change from baseline, and percent change from Baseline PPi, PLP, PL, PA versus time profiles values will be listed by treatment, sampling time and participant. Listings will include actual sampling times relative to dose administration, observed PPi, PLP, PL, PA versus time profiles value, change from baseline value, and percentage change from baseline. Baseline will be taken as the last measurement prior to dosing, see Section 6.1 Descriptive statistics (number, mean, SD, CV%, minimum, median, and maximum) will be presented by dose cohort, including pooled placebo, pooled active treatment across cohorts, pooled IV cohorts, pooled SC cohorts and overall for absolute, and percentage change from baseline PD assessment, time of minimum and time of maximum will only have minimum, maximum, and median time.

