Urinalysis (via dipstick)			Х	Х	Х	Х	Х	Х	Х
Urine pregnancy test ^e						Х			
Serum pregnancy test ^e								Х	Х
РК	Х	Х	Х	Х	Х	Х	Х	Х	Х
PD (PPi, PLP, PL, and PA)			Х	Х	Х	Х	Х	Х	Х
Immunogenicity samples ^f						Х		Х	Х
Urine for calcium, phosphorus, and creatinine ^g			Х	Х		Х		Х	Х
Hypersensitivity reactions ^h	$\leftarrow Monitor \ continuously \ after \ dose \rightarrow$								
Hypersensitivity reaction laboratory tests (tryptase and complement C5b-9) ⁱ	$\leftarrow See \text{ footnote}^h \rightarrow$								
Concomitant medications	$\leftarrow Monitor \ continuously \ (after \ ICF \ is \ signed \ at \ Screening) \rightarrow$								
Adverse event review and evaluation	←Monitor continuously (after ICF is signed at Screening)→								

ALXN1910-HV-101

Statistical Analysis Plan

Note: When scheduled at the same timepoint, the triplicate ECG should be performed first, followed by vital signs assessments, and then PK/PD sampling.

^a Permitted windows for study assessments are described in the Windows Allowance Document.

^b EoS procedures will be performed on Day 75.. If possible, participants who withdraw/are withdrawn from the study should have an ED visit conducted at the time of discontinuation that includes the EoS assessments. All efforts will be made to contact participants who ED from the study via phone for a safety follow-up call approximately 30 days (4.5 half-lives) after their dose to assess AEs.

^c Vital signs taken postdose will be performed before the coinciding blood collection, whenever possible.

^d Each ECG will be 12-lead and performed in triplicate sequentially within 5 minutes, at least 1 minute apart after 10 minutes of bedrest in supine position (note, no bedrest is required post ECG). ECGs should not be assessed after any major meal (i.e., major meals should be withheld until after ECG assessments).

^e Only female participants of childbearing potential will have a pregnancy testing to confirm the participant is not pregnant.

^f Sample for ADA assessments will be collected prior to administration of the drug. In the event of suspected SAE like hypersensitivity or anaphylaxis, additional samples may be collected for ADA assessments at or near the event.

^g Spot urine collection.

^h See Protocol Section 10.4 for details.

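### Japanese versus non-Japanese PD comparison: a geometric mean of change from baseline fails once any change is zero or negative, and the first-choice unstructured covariance has no finite likelihood maximum with 12 participants and 10 visits

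*SAP*

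**What the plan says.** SAP 4.12.5.1 compares Cohort 2 with Cohort 4 on active treatment, using a repeated-measures model with cohort, visit and "cohort by visit interaction as fixed effects, participant as a random effect, and baseline value as a covariate". On covariance it says "The unstructured covariance structure will be employed; however, if the model fails to converge, Toeplitz, heterogeneous compound symmetry", with compound symmetry (CS) next and, if every structure fails, an analysis of variance with baseline and cohort.

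For the descriptive part of the same comparison, "the geometric means and the associated 95% CIs of difference of PD parameters in observed value and CFB value will be reported". Protocol 9.4.2.2 says the same on both matters.

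On size, "8 participants will be randomly assigned in a 3:1 ratio to treatment and placebo in each of the 6 cohorts" (SAP 3.1). The PD visits are in the row starting "PD (PPi, PLP, PL, and PA" of the schedule (Protocol 1.3, repeated in SAP 6.1). SAP 6.5 gives sample code for three PK analyses but none for this PD model.

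**The concern.** A geometric mean needs strictly positive values. Concentrations meet that condition; changes from baseline need not. The plan gives no rule for a zero or negative change, so the programmer would have to leave the cell empty, drop the offending values or shift the data. Dropping them would keep only the participants whose marker rose.

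The unstructured model asks a very small data set for a full 10 x 10 covariance matrix, and adds a participant variance that such a matrix already contains. If the likelihood has no maximum, no valid estimate exists at that step. Whether the plan moves on then depends on whether the software reports non-convergence.

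At stake is the model-based answer to the PD part of a secondary objective, for four markers (PPi, PLP, PL and PA).

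**Working it through.** **The plan's own figure.** The only computed sample-size figures are the adverse event probabilities in Protocol 9.2 and SAP 3.2. The formula 1 - (1 - p)^6 gives 46.9, 62.3, 73.8, 82.2, 88.2, 92.5 and 95.3% for p from 10% to 40%, as printed. This confirms 6 active participants per cohort. No figure is given for the PD model.

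**Inputs.**
- Participants: 8 x 3/4 = 6 active per cohort, so 6 + 6 = 12. The PD Set (SAP 4.4.1) can lower this, and missing values are not imputed (SAP 4.16).
- Post-dose PD visits: 24, 48 and 96 h, then Days 8, 15, 22, 29, 36, 43 and 75, so 3 + 7 = 10. The predose sample is the baseline.
- Fixed effects: 2 x 10 cohort-by-visit means + 1 baseline slope = 21.
- Unstructured covariance: 10 x 11/2 = 55 parameters, from at most 12 x 10 = 120 observations.

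**Geometric mean of CFB.** Let d be mean change divided by SD. With normal, independent changes (assumed), P(all 6 positive) = Phi(d)^6:
- d = 0: 0.5^6 = 1.6%
- d = 1: 0.8413^6 = 35%
- d = 2: 0.9772^6 = 87%

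The documents give no PD effect size or SD, so d is shown as a range. If CFB is summarised by visit, there are 2 cohorts x 10 visits x 4 markers = 80 cells. Even with d = 2 in every cell, about 80 x (1 - 0.871) = 10 cells would be expected to have no geometric mean.

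**Unstructured covariance.** Removing the cohort means leaves 12 - 2 = 10 contrasts. Let R (10 x 10) hold these contrasts for the outcomes and v those for baseline. The residual matrix at common slope b is R - b v 1'. Its determinant, det(R)(1 - b 1'R^-1 v), is linear in b and is zero at b* = 1/(1'R^-1 v). At that slope one direction across the visits has zero residual variance. As its eigenvalue L shrinks to 0:
- ML contains -(12/2) ln L and rises by 6 x ln(100) = 27.6 per 100-fold shrinkage.
- REML contains -(10/2) ln L + (1/2) ln L = -4.5 ln L and rises by 4.5 x ln(100) = 20.7.

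Neither has a maximum. In simulated 12 x 10 data, REML rose by a median of 20.7 (minimum 20.6) in 200 of 200 sets. With 13 complete participants there was no rise on the same path (0 of 100). The result is algebraic and does not depend on the simulated covariance. A finite maximum needs 13 participants with all 10 values, or at most 9 visits with 12.

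**Replacement.** Protocol 7.3 says "subsequent participants in that cohort to withdraw/be withdrawn before EOS completion will be replaced". That reaches 13 complete profiles only if the withdrawn participant also has all 10 values, meaning withdrawal after Day 43 with the early-discontinuation sample counted as Day 75. SAP 6.1 says such participants "should have an ED visit conducted at the time of discontinuation that includes the EoS assessments" but does not say how that value enters the model. With another visit missing, REML still rose in 297 of 300 sets; the other 3 had not reached the limit.

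**Participant random effect.** With a participant variance added, the identifiable covariance parameters are 55 of 56 (unstructured), 10 of 11 (Toeplitz), 2 of 3 (CS) and 11 of 12 (heterogeneous CS at equal visit variances; 12 of 12 only when they differ).

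**Trigger.** On this REML likelihood, one general-purpose optimiser (BFGS) reported convergence in 0 of 20 sets. Another (L-BFGS-B) did so in 20 of 20, at smallest-to-largest eigenvalue ratios of 6e-14 to 1.3e-9.

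**Effect of a degenerate fit.** The limit was simulated with slope b*, residual cross-products divided by 10, t with 10 df, 14 assumed correlation patterns and 4,000 sets each. Coverage of 95% CIs for the cohort difference was 93.1-95.6% at single visits and 93.1-95.1% for the visit average. A separate repeat gave about 93.4-95.2%. The Day 75 interval was a median 1.04-1.72 times as wide as a single-visit analysis of covariance.

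**Fallback structures.** Coverage with Kenward-Roger df over 14 assumed patterns (Toeplitz: 7 equal-SD patterns only); Monte Carlo SE about 1.3 points, Toeplitz about 2:

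| Structure | Visit-averaged difference | Day 75 |
|---|---|---|
| Toeplitz | 93.7-95.8% | 89.4-97.6% |
| Heterogeneous CS | 92.8-96.8% | 93.1-97.9% |
| CS | 92.0-97.6% | 87.8-99.7% |

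Heterogeneous CS intervals for the averaged difference were up to 2.8 times as wide as those under CS.

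**The case against.** The strongest reply is that the plan never relies on the unstructured fit. It names three simpler structures and an analysis of variance, and a likelihood without a maximum is a non-converging model in the ordinary sense. The plan's software is SAS (SAP 4.3), which was not tested, and flags from general-purpose optimisers with numerical gradients say little about it. This largely stands: the ladder is a real safeguard, and its failure is a possibility that has not been demonstrated in SAS. What remains is that the wording does not cover a fit that is reported as converged but is singular.

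A reader might also infer that a near-singular fit would make the reported differences and CIs invalid. The coverage check does not support that for cohort differences. What it shows is lost precision and a baseline slope set by an accident of the data rather than estimated. The check is neither SAS nor Kenward-Roger, and it does not cover joint interaction tests.

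On geometric means, SAP 4.12.5 already plans arithmetic summaries: "Descriptive statistics (number, mean, SD, CV%, minimum, median, and maximum) will be presented by dose cohort". The defect might therefore be caught in programming, and output shells not seen here might contain a rule. Even so, the statistic named for the ethnicity comparison is the one that can fail, and neither document supplies a rule.

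**Conclusion.** Both points hold as errors of specification, with modest impact. The comparison is secondary and descriptive, no hypothesis is tested (Protocol 9.1), and the primary safety objective is untouched.

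The geometric mean of CFB is wrong for any marker with a zero or negative change. The percentages rest on assumed normal, independent changes; the undefined statistic does not. It is tempting to say that PPi will certainly fall and so make the calculation impossible, but that is only an inference from the mechanism in Protocol 2.2.

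The unstructured step has no finite ML or REML maximum under the planned numbers, and the participant random effect is not identifiable beside it. Two stronger readings fail. The comparison is not left without a usable model, because the ladder contains estimable ones. Nor do the documents show that heterogeneous CS must come before Toeplitz: that depends on correlations they do not give, and the simulated coverage does not settle it.

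**What to change.** 1. For CFB, replace geometric means with arithmetic means and differences. If a geometric summary is wanted, report the geometric mean ratio to baseline and the Japanese/non-Japanese ratio, from ln(PD) with ln(baseline) as covariate. Geometric means of observed concentrations can stay.
2. Either go directly to the existing fallback structures, or keep the ladder and define its trigger as non-convergence or a singular or non-positive-definite covariance or Hessian. The order of the remaining structures is the sponsor's choice and should be fixed in advance.
3. State that participant is the repeated-measures subject, with no additional participant random effect.
4. Record the changes in SAP 4.19 as departures from Protocol 9.4.2.2, as was done for the antibody titer categories.

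The cost is SAP wording, PD code and that entry. SAP section 1 allows updates when an analysis proves inappropriate and says how to document changes after finalisation. The statistical downside is that a simpler covariance may be misspecified, with coverage and precision varying as tabulated above.

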3.2 Determination of Sample Size

No formal testing of hypotheses has been planned for this study. Therefore, no formal sample size calculations were performed. Approximately 48 participants are considered to be adequate to support and analyze the initial characterization of safety, tolerability, PK, PD, and immunogenicity for ALXN1910. The following table provides the probability of observing AEs under various underlying event incidence.

Incidence of AE in the Population	Probability to Observe at least 1 AE Occurrence in 6 Participants from Each Cohort
10%	46.9%
15%	62.3%
20%	73.8%
25%	82.2%
30%	88.2%
35%	92.5%
40%	95.3%

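### The Japanese versus non-Japanese PD model adds a participant random effect that three of its four covariance structures cannot identify, and its last fallback does not say that it is fitted at each visit

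*SAP*

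**What the plan says.** SAP 4.12.5.1, with near-identical wording in Protocol 9.4.2.2, says that PD "will be evaluated over time for Japanese and non-Japanese participants (Cohort 2 versus Cohort 4) on active treatment". The main analysis is an "MMRM model with cohort, visit, and cohort by visit interaction as fixed effects, participant as a random effect, and baseline value as a covariate". Four covariance structures are tried in order until one converges: unstructured, Toeplitz, heterogeneous compound symmetry, compound symmetry. "In the case that all covariance structures fail to converge", then "the analysis of variance statistical model with baseline and cohort as the fixed effects will be used".

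Neither document says whether this last model is fitted at each visit, to one summary value per participant, or to all visits together. SAP 6.5 gives sample code for three PK analyses and none for PD. Whatever the model does, SAP 4.12.5.1 also plans descriptive comparisons of the two cohorts, with geometric means and 95% CIs of difference for observed values and change from baseline.

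**The concern.** There are two linked specification problems.

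First, an MMRM normally carries the within-participant correlation in the residual covariance matrix. A participant random effect on top of that matrix adds a parameter that most of the listed structures already contain. The likelihood is then flat in one direction. A fit may stop without converging, and the analysis moves down the list for a reason unrelated to the data.

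Second, the end of the list is loosely worded. The stated question concerns a difference over time, but the fallback keeps only baseline and cohort. A programmer who drops the other terms and runs the model on the same longitudinal dataset would treat repeated values as independent and obtain one average cohort difference. The interval would have unreliable coverage, and the result would not show when the cohorts differ.

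The PD comparison between Japanese and non-Japanese participants is a stated secondary objective, and Protocol 2.1 and 5.3 tie the Japanese cohort to ICH E5.

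**Working it through.** **Counts.** SAP 3.1: "8 participants will be randomly assigned in a 3:1 ratio to treatment and placebo in each of the 6 cohorts". That is 8 × 3/4 = 6 active per cohort, so 12 active in Cohorts 2 and 4. The plan's own table agrees: its column is headed "Probability to Observe at least 1 AE Occurrence in 6 Participants from Each Cohort", and 1 − (1 − p)^6 reproduces all seven entries (for example 1 − 0.9^6 = 46.9% and 1 − 0.6^6 = 95.3%). In Protocol 1.3 the row "PD (PPi, PLP, PL, and PA") shows a predose sample, then 24, 48 and 96 h, then Days 8, 15, 22, 29, 36, 43 and 75. That is 3 + 7 = 10 post-dose times, and 12 × 10 = 120 values per analyte with complete data.

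**Identifiability.** A participant variance adds the same constant to every entry of the 10 × 10 covariance matrix. I counted the parameters of each structure with that variance added, and the rank of the matrix of covariance derivatives.

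| Residual structure | Parameters alone | With participant variance | Rank |
|---|---|---|---|
| Unstructured | 10 × 11/2 = 55 | 56 | 55 |
| Toeplitz | 10 | 11 | 10 |
| Heterogeneous compound symmetry | 11 | 12 | 12 |
| Compound symmetry | 2 | 3 | 2 |

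Three of the four are short by exactly one. Heterogeneous compound symmetry escapes only while the visit variances differ; if they are equal, it reduces to compound symmetry. Separately, the unstructured matrix needs 55 parameters from 12 participants, with 12 − 2 = 10 participant-level degrees of freedom for a 10 × 10 matrix. Protocol 7.3 allows the first withdrawal in a cohort to go unreplaced.

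**Coverage of the fallback.** The documents give no within-participant correlation and no PD profile, so both are assumptions. The simulations use 6 v 6 participants, 10 visits and no true cohort difference. Correlation is exchangeable and taken after baseline adjustment, and visit effects are in SD units. The entries are the share of trials in which the 95% CI from one fit to all 120 rows misses the true value.

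| Visit effects | ρ = 0.1 | 0.3 | 0.5 | 0.7 |
|---|---|---|---|---|
| None | 15% | 32% | 44% | 52% |
| SD 0.5 | 11% | 27% | 36% | 44% |
| SD 1 | 4.5% | 16% | 23% | 31% |
| SD 2 | 0.05% | 2% | 7% | 10% |

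With an early effect that decays to zero, at ρ = 0.5, the miss rate is 42% with no effect, 29% at a peak of 2 SD, 20% at 3 SD and 11% at 4 SD. The same baseline-and-cohort model fitted at one visit (12 rows, 9 residual degrees of freedom) misses in about 4% to 6% of trials throughout.

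Two forces explain the pattern. Ignoring correlation makes the interval too narrow, by about 1/√(1 + 9ρ). Omitting visit puts the visit-to-visit change into the residual and widens it.

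As a check, a separate run set the raw correlation to 0.5 with baseline included and no visit effects. The adjusted correlation is then (0.5 − 0.25)/(1 − 0.25) = 0.33, and 1/√(1 + 9 × 0.33) = 0.50. The t quantiles on 117 and 9 degrees of freedom have ratio 1.98/2.26 = 0.88, so the expected width ratio is 0.50 × 0.88 = 0.44. The simulation gave 0.43 and a miss rate of 32%, in line with the table at ρ = 0.3.

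**The case against.** The strongest reply is that the fallback is a visit-by-visit ANCOVA. A model with only baseline and cohort is the natural form of one: each fit has one row per participant, needs no visit term and cannot estimate a participant effect. Protocol 9.4 plans summaries by visit where applicable. On that reading coverage is correct and the comparison is still shown over time. This stands. A reader might infer that the plan does pool 120 values, but neither document says so. What remains is that the sentence permits it, while SAP 4.13.3, 4.13.5 and 4.14 do specify visits for other summaries, and no PD code settles the matter.

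The second reply is that the fallback may never be reached. A flat likelihood is not proof of non-convergence, software may set a redundant variance to zero and carry on, and one of the four structures is usually identifiable. The phrase about participant may only name the correlated unit. This also stands: no convergence failure was simulated, and how often the fallback would be used is unknown. A literal coding is still credible, because the SAP 6.5 code for bioavailability and ethnicity puts a participant random effect on PK parameters with one value per participant.

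The third reply is that the miss rates depend on the visit profile as much as on the correlation. That is correct, and with small correlation and large visit effects the pooled interval is too wide. It does not defend the pooled fit, whose coverage would depend on visit variation that the model ignores.

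Finally, the listings, summaries and profile plots in SAP 4.12.5 and the descriptive comparisons would still let a reader see an early difference.

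**Conclusion.** Both points hold as defects of specification. The participant random effect, coded as written, is redundant with the unstructured, Toeplitz and compound symmetry structures; this is exact and needs no assumption about the data. The last fallback is under-specified, and one permitted reading is invalid. That reading gives one average difference in place of a comparison over time. For correlations of 0.1 to 0.7 and the visit profiles above, its 95% CI misses in roughly 2% to 52% of trials, and in under 1% where correlation is 0.1 and visit effects are very large. A per-visit fit misses in about 5%. The figures rest on assumed correlations and profiles and on complete data.

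It would be too strong to call this an inflated type I error: Protocol 9.1 says that no hypotheses are tested, so the issue is interval coverage. Nor do the documents show that the list of structures will fail. The reach is part of one secondary objective, under a contingency. The change is worth making because it costs almost nothing and removes the invalid reading.

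**What to change.** In SAP 4.12.5.1 and Protocol 9.4.2.2:

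- Delete participant as a random effect from the MMRM. State that the within-participant covariance is modelled by the residual structure alone, with participant as the subject of the repeated measures. The list then ends at a two-parameter compound symmetry model that is identifiable.
- Replace the last fallback with wording such as: if no covariance structure converges, an ANCOVA with baseline and cohort will be fitted separately at each post-dose visit, reporting the cohort difference and its 95% CI per visit; values from different visits will not be pooled in one model.
- Add the PD model code to SAP 6.5.

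The cost is a few sentences and a by-visit statement in the program, with no new data. If the fallback is used, the intervals will usually be wider than a pooled fit would give. If the sponsor already intended a per-visit fit, the edit to the fallback changes only the clarity of the text.
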